### **3.2 STUDY PROCEDURES**

Refer to the study flow chart (Section 1.7) for a concise view and timing of the study procedures.

#### **3.2.1 Visit Windows**

Each dose of V212 or placebo should be administered every ~30 days. There is a minimum of 20 days of postvaccination follow-up required prior to the subsequent dose of vaccine. The allowable window between each vaccine dose is 20 to 40 days. The minimum follow-up period postvaccination dose 4 is 28 days; the maximum allowable window at Visit 5 is 60 days postvaccination dose 4. Deviations from the permitted visit windows (i.e., the patient meets deferment criteria or the patient is not able to complete the visit as scheduled per protocol because of medical or logistical reasons) require consultation between the investigator and the SPONSOR and written documentation of the collaborative decision on patient management. All study procedures should be performed at the vaccination visits.

#### **3.2.2 Informed Consent**

Study personnel must obtain written informed consent from each patient prior to performing any study procedures (e.g., collection of blood sample, vaccination, or rash lesion sample) Consent must be documented by obtaining the dated signatures of both the patient and the person conducting the consent discussion, on the consent form. A copy of the signed and dated consent form will be given to the patient for his/her records.

Should a patient sign a consent form but not enroll in the study on that same day (i.e. no study procedures are performed) that signed consent form would be valid for up to 14 days. If the patient returns after more than 14 days have elapsed, consent procedures must begin again and a new written consent must be obtained.

### **3.2.3 Assignment of Baseline Number**

Baseline numbers will be automatically generated by the SPONSOR via an electronic data management system. Each patient will be assigned a unique baseline number immediately after the informed consent is signed. The baseline number identifies the patient for all study-related procedures that occur prior to receiving an allocation number. Baseline numbers are a combination of the site number and the patient number and are assigned sequentially from the lowest number to the highest number at each site. Baseline numbers should never be skipped and may not be reassigned for any reason. A single study patient cannot be assigned more than 1 baseline number.

### **3.2.4 Non-Randomized Patients**

If a patient has signed a consent form, but the patient is not randomized, the patient's basic demographic information and the reason(s) for exclusion from the study must be reported. The baseline number previously assigned to the patient should be used to uniquely identify this nonrandomized patient. For detailed information on entering data into the data collection system for these patients, consult the electronic data capture (EDC) data entry guidelines provided by the SPONSOR.

### **3.2.5 Study Participation Patient Identification Card**

All subjects/patients will be given a card, at the time of screening, identifying them as participants in a research study. The card will contain contact information (including direct telephone numbers) to be utilized in the event of an emergency.

### **3.2.6 Physical Examination**

A physical examination, **including weight**, will be performed at Day 1 by a physician, nurse practitioner, or physician's assistant (in accordance with local law) and will include a general review and evaluation of body systems to determine whether the patient meets enrollment criteria for this study. Physical examination details will be documented in the patient's chart.

### **3.2.7 Medical History/Conditions**

The patient's medical conditions during the 5 years prior to enrollment should be reported, capturing any chronic or serious conditions. In addition, the primary cancer diagnosis, type of malignancy, grade, and stage or classification of disease should also be collected and entered into the database.

### 3.2.8 History of Varicella-Zoster Virus Infection

To be enrolled in the study, patients must have a prior history of varicella, antibodies to VZV (documented prior to receipt of blood products), or residence in a country with endemic VZV infection. A validated list of countries where VZV is considered endemic does not exist. Operationally, VZV is assumed to be endemic in countries where chickenpox is a typical childhood disease. Patients who reside in regions that have implemented universal varicella vaccination programs will be considered to have resided in endemic regions if they attended school in an endemic region where varicella vaccination had not yet been widely implemented. In areas of the world where it is uncertain if VZV is endemic, study sites are encouraged to perform VZV antibody testing (local laboratory) of potential study participants prior to administration of blood products consistent with standard medical practice. VZV seronegative patients should not be enrolled.

### 3.2.9 Concomitant Medication(s)/Treatment(s)

Specific prohibited medications/treatments in this study include the following:

- Live virus vaccines at any time beginning 4 weeks prior to dose 1 through 28 days postvaccination dose 4;
- Any varicella or non-study zoster vaccine for the duration of the study;
- Inactivated vaccines beginning 7 days prior to through 7 days following any dose of vaccine or placebo.
  - Thus, inactivated influenza vaccines should not be administered in the time period beginning 7 days prior to through 7 days following any dose of study vaccine or placebo. It is understood that this study will be conducted over multiple influenza seasons. The allowed window for administration of inactivated vaccines should be sufficient to allow for administration of inactivated influenza vaccines. *Of important note, Live influenza vaccine is prohibited at any time beginning 4 weeks prior to dose 1 through 28 days postvaccination dose 4.*
- Receipt of any long term antiviral prophylaxis (duration greater than 4 weeks) with activity against HSV, VZV, or CMV.

All medications, including standard antiviral therapy and pain medications administered for HZ treatment of a HZ case will be permitted as clinically indicated. Other prescription or over-the-counter medications that may be required for pre-existing or concurrent conditions may be used during the study. Chemotherapeutic regimens and/or radiotherapy may be used throughout the study.

It is imperative that all medications administered to the patient 90 days prior to enrollment and any new medications or procedures (e.g. radiation therapy, blood transfusions, chemotherapy, etc.) starting/occurring *through 28 days Postvaccination* 4 be recorded.

Medications administered for the treatment of HZ and/or HZ symptom relief, and those medications administered within 14 days of an SAE, and as treatment for an SAE, will be collected for the *duration of the study*.

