- † Monthly efficacy contact by telephone, via the internet, or during a study visit will be required for each patient for the duration of the study to assess for occurrence of unreported symptoms of suspected HZ. At Visit 5, site personnel will assist the patient with the first efficacy contact using the IVRS via the internet or via phone.
- ‡ Beginning 3 months following Visit 5 and continuing every 3 months for the duration of the study, patients will be contacted by site personnel, and using a pre-defined script, patients will be queried as to whether all serious adverse experiences have been reported since last contact. Concomitant medications administered as a result of any SAE for the duration of the study will also be collected. Information obtained from this contact will facilitate accurate and timely reporting of SAEs
- § Study will continue until the required number of cases of herpes zoster (HZ) has accrued, or if the decision is made to terminate the study or one arm early following a recommendation made by the DMC based on safety concerns or futile efficacy results from the interim futility analysis or if the trial is declared infeasible. At that time, the study or arm will begin to enter the close-out phase and no additional suspected HZ cases will be accrued. Patients already entered in suspected HZ case follow-up will complete their 6-month HZ assessment period. In the event the study or arm is terminated sooner than 1 year after the last vaccine dose is administered in this study, the study will continue to allow all patients to complete a minimum of 1 year post-vaccination follow-up for safety and efficacy. All patients enrolled in the study will be contacted by telephone to complete the study close-out questions.
- || The allowable window between each vaccine dose is 20 to 40 days. All study procedures must be performed at the vaccination visit. Visit window permitted for Visit 5 is 28 to 60 days Postdose 4. Every attempt should be made to schedule the patient's Postdose 4 follow-up visit as close to day 28 Postdose 4 to assure for accurate and timely safety reporting. Deviations from the permitted visit windows (i.e., the patient meets deferment criteria or the patient is not able to complete the visit as scheduled per protocol because of medical or logistical reasons) require consultation between the investigator and the SPONSOR and written documentation of the collaborative decision on patient management.

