8. Patients with STM will be eligible for enrollment if they have not received (nor are expected to require receipt of) blood products within 3 months prior to enrollment through 28 days Postvaccination 4.

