## **2.3 PATIENT EXCLUSION CRITERIA**

An individual will not be eligible to participate in this study if any of the following criteria apply:

1. A history of allergic reaction to any vaccine component (including gelatin) or an anaphylactic/anaphylactoid reaction to neomycin (a history of contact dermatitis to neomycin is not a criterion for study exclusion).
2. Prior history of HZ within 1 year of enrollment.
3. Prior or expected receipt of any varicella or non-study zoster vaccine.
4. Patient is currently receiving or expected to receive long-term antiviral prophylaxis (greater than 4 weeks duration) with activity against herpes simplex virus (HSV), VZV or cytomegalovirus (CMV).
5. Patient is pregnant or breastfeeding or expecting to conceive within the period of 2 weeks prior to enrollment throughout 6 months after last vaccination dose.
6. Any live virus vaccine administered or scheduled in the period from 4 weeks prior to Dose 1 through 28 days postvaccination dose 4.
7. Any inactivated vaccine administered or scheduled within the period from 7 days prior to, through 7 days following, any dose of study vaccine.
8. Unlikely to adhere to the study procedures or attend study visits.
9. Any other reason that in the opinion of the investigator might interfere with the evaluation required by the study.
10. Patients with STM will be excluded from study if they have received (or are expected to require receipt of) blood products within 3 months prior to enrollment through 28 days Postvaccination 4.

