### **3.4 SAFETY MEASUREMENTS**

#### **3.4.1 Clinical Measurements for Safety/Vaccination Report Card**

##### **3.4.1.1 Safety Follow-up During the Vaccination Period**

Each patient will receive a VRC at Visits 1, 2, 3, and 4. On the VRC, patients will be asked to record daily oral temperature measurements on the VRC. Patients should take oral temperature measurements using only the SPONSOR provided standard oral thermometer. Temperature measurements via the otic or axillary methods are not permitted. Patients will also be asked to record on the VRC all adverse experiences during the primary safety follow-up period (postvaccination dose 1 through 28 days postvaccination dose 4), including injection-site adverse experiences and systemic adverse experiences occurring from Day 1 through 28 days postvaccination dose 4. Patients will be asked to record on the VRC any rash at the injection site, as well as any varicella/varicella-like or HZ/HZ-like rashes postvaccination Day 1 through 28 days postvaccination dose 4. Any vaccines other than study vaccines and any medications that are administered during that period should also be documented on the VRC.

The patient will be asked to bring the VRC to the study site at the next scheduled visit. Study personnel will review the VRC for completeness, accuracy, and clarity at each scheduled visit from Visit 2 through Visit 5. All comments are to be reviewed by study personnel and discussed with the patient for clarification, as necessary. Any information gained during VRC review with the patient should be clearly documented, initialed, and dated at the bottom of the VRC. The VRC is considered a source document and no original information recorded by the patient should be crossed out or altered in any manner by study personnel.

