### **3.5.4.2 Immunogenicity Analysis Populations**

#### **Per Protocol Immunogenicity (PPI) Populations**

The immunogenicity summaries and analyses will be provided for the PPI population. To be included in this population, patients must:

- (1) Have received all 4 vaccination doses
- (2) Have not reported any exposure to varicella/HZ within 4 weeks prior to blood draw
- (3) Have not develop any suspected varicella/HZ before the relevant blood sampling
- (4) Have not received medical treatments (such as blood products, immunoglobulin therapy) that may interfere with one or both of the proposed immunogenicity measurements.

Based on criterion (4), some patients may be excluded from only one of the 2 immunogenicity analysis (gpELISA, ELISPOT). The final determination of patients excluded from one or both immunogenicity analyses, and thereby the composition of the Per Protocol immunogenicity analysis populations, will be made prior to the final unblinding of the database and will be documented in a separate memo.

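### Routine recording of transfusions and immunoglobulin stops 28 days after Dose 4, but the Visit 5 gpELISA sample may be drawn up to day 60, so the exclusion for interfering treatments cannot be applied reliably between day 29 and the draw

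*Combined protocol and SAP*

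**What the plan says.** **Recording.** Section 3.2.9 asks for all medications from 90 days before enrollment, and for new medications or procedures "starting/occurring *through 28 days Postvaccination* 4 be recorded". Transfusion is one of its examples. The patient diary (VRC) covers the same period: in 3.4.1.1, "any medications that are administered during that period should also be documented on the VRC", where the period ends 28 days after Dose 4. Beyond that, 3.2.9 keeps two routes open: medications for HZ or its symptoms, and "those medications administered within 14 days of an SAE, and as treatment for an SAE, will be collected for the *duration of the study".

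**Draw.** Under 3.2.1, "the maximum allowable window at Visit 5 is 60 days postvaccination dose 4". The flow chart in 1.7 agrees ("Visit window permitted for Visit 5 is 28 to 60 days Postdose 4") and asks sites to aim as close to day 28 as they can.

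**Exclusion.** PPI criterion 4 in 3.5.4.2 requires that patients "Have not received medical treatments (such as blood products, immunoglobulin therapy) that may interfere with one or both of the proposed immunogenicity measurements". Section 3.5.5.2 drops the gpELISA measurement at the affected time point and any later one. It keeps immunoglobulin recipients in the ELISPOT analysis.

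**Eligibility.** Inclusion criterion 8 in 2.2 reads "Patients with STM will be eligible for enrollment if they have not received (nor are expected to require receipt of) blood products", and exclusion criterion 10 in 2.3 is its mirror image, covering "blood products within 3 months prior to enrollment through 28 days Postvaccination 4". Both apply to STM patients only, and neither names immunoglobulin. Blood products are not on the list of prohibited treatments in 3.2.9.

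**The concern.** The exclusion depends on knowing what the patient received before the sample. Routine collection of that information ends on the first day on which the sample may be taken. An STM patient transfused as an outpatient on day 35 and sampled on day 50 may have no record of the transfusion, and would then enter the PPI analysis as if criterion 4 were met.

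The plan itself treats this source of error as important. Section 3.1.2.4 gives it as the reason for not running gpELISA in the hematologic malignancy (HM) population at all: the disease and its treatments, blood products among them, can bias an antibody assay. STM patients enter while on chemotherapy, which may continue throughout the study.

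Passively acquired antibody could be read as a response to vaccination. It would enter the GMT, the GMFR, the proportions with 2-, 3- and 4-fold rises, the proportion at or above 400 gpELISA units/mL, and the marker used in the Cox model for HZ risk.

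**Working it through.** The plan states no figure to reproduce here. The check compares windows.

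**Inputs**
- Last day of routine recording: day 28 after Dose 4 (3.2.9; same end for the VRC in 3.4.1.1).
- Permitted draw day *d*: 28 to 60 (1.7, 3.2.1).
- Treatments still collected after day 28: those for HZ and those linked to an SAE (3.2.9).

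**Formula.** Days before the draw outside routine recording = max(0, *d* − 28).

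| Draw day | Unrecorded days | Share of the 28 days before the draw |
|---|---|---|
| 28 | 0 | 0% |
| 35 | 7 | 25% |
| 42 | 14 | 50% |
| 49 | 21 | 75% |
| 56 | 28 | 100% |
| 60 | 32 | 100% |

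The maximum is 32 days, or 32/7 = 4.6 weeks. From day 56 on, the whole four weeks before the sample lie outside routine recording. The 28-day column is only a yardstick; criterion 4 states no look-back period.

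**Does another rule close the gap?**
- *Adverse experience forms.* Under 3.4.2, non-serious events are collected only to 28 days after the last dose, so a non-serious event leading to a transfusion leaves no trace there either.
- *SAE route.* Table 3-1 makes an inpatient admission serious unless it is for a pre-existing condition that has not worsened. Treatments around most admissions should therefore be captured, if the word medications is read to include transfusions. Outpatient use without an SAE is not captured.
- *Visit 5 questions.* Section 3.2.16 asks at Visit 5 about varicella or HZ exposure since the previous visit, so PPI criterion 2 is covered up to the visit. No matching question exists for blood products or immunoglobulin.
- *Supportive analysis.* Section 3.5.5.2 allows an analysis of all valid results regardless of deviations. It cannot identify treatments that were never recorded.

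Nothing closes the gap for a treatment given after day 28 without a link to HZ or an SAE.

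**Reach.** gpELISA is run only in STM (about 2696 patients planned). Immunoglobulin recipients stay in the ELISPOT analysis, so the immunoglobulin part of the gap concerns gpELISA alone.

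**The case against.** The strongest reply is that the gap is narrow and the consequence small. Much of this stands. Sites are told to aim for day 28, and a day-28 draw has no gap. The exclusion works fully for every treatment up to day 28. HZ- and SAE-linked medications are collected for the whole study. STM patients were selected as not expected to need blood products in the period to day 28. Every immunogenicity analysis is exploratory. Criterion 4 itself has no end date, and PPI membership is settled in a memo before unblinding, so the rule could reach the draw if the data existed. None of this supplies the missing records.

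A reader might infer three stronger things that the documents do not support.

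- *That both treatments are barred up to day 28.* Immunoglobulin is barred nowhere by name. Blood products appear only as an STM eligibility criterion.
- *That the exclusion is inoperable.* It is unreliable only for the interval from day 29 to a later draw, and only for treatments outside the HZ and SAE routes.
- *That the vaccine-to-placebo fold difference is diluted by a known amount.* Suppose a share *s* of each arm has its titer multiplied by *f*. Each GMT is then multiplied by *f*^*s*. With assumed values this runs from 2^0.03 = 1.02 to 10^0.05 = 1.12. If *s* and *f* are equal in the two arms, the factor cancels in the GMT ratio. Dilution needs unequal use, or passive antibody that adds a similar amount in both arms and so raises lower placebo titers proportionally more. Even with no rise at all in vaccinees, these inputs bound the effect on the ratio by the same factor of 1.02 to 1.12. The shares and folds are assumptions with no source in the documents.

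**Conclusion.** The point holds as a mismatch between a recording rule and an exclusion that depends on it. For Visit 5 draws after day 28, PPI criterion 4 and the gpELISA exclusion in 3.5.5.2 cannot be applied reliably to the last 1 to 32 days before the sample.

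It mainly affects the exploratory gpELISA results in STM: GMT, GMFR, the fold-rise and 400 units/mL proportions, and the association with HZ risk. The primary, secondary and safety analyses do not use these data and are unaffected.

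The length of the gap follows from the stated windows and needs no assumption. The effect on the estimates cannot be computed: it would need the distribution of draw days and the frequency of unrecorded blood-product or immunoglobulin use. The practical consequence is that, for late draws, the sponsor could not show that the PPI set meets its own definition.

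**What to change.** In 3.2.9, extend recording of blood products and immunoglobulin to the date of the Visit 5 blood draw, and state in 3.5.4.2 that criterion 4 applies up to that date. For patients already sampled after day 28, retrieve the dates of any such treatment between day 29 and the draw from the chart before PPI membership is fixed in the pre-unblinding memo.

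Inclusion criterion 8 and exclusion criterion 10 need no change. Section 3.1.2 says that no additional STM subjects will be enrolled, so a change to eligibility would do little, and the problem is one of recording.

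The cost is a later end date for two kinds of entry (at most 32 more days per patient), a chart check limited to patients drawn after day 28, and slightly fewer patients in the PPI population. With recording up to the draw, the unrecorded interval becomes 0 days for every patient.

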### **3.2.10 Contraception**

Women who are not of reproductive potential are not required to use contraceptive methods in this study. A female patient who is not of reproductive potential is defined as: one who has either (1) reached natural menopause (defined as 6 months of spontaneous amenorrhea with serum follicle stimulating hormone [FSH] levels in the postmenopausal range as determined by a laboratory, or 12 months of spontaneous amenorrhea), (2) post-surgical bilateral oophorectomy and/or hysterectomy, or (3) bilateral tubal ligation. Note that the definition surrounding the term "natural menopause" as it relates to 6 or 12 months of amenorrhea is specific to women who are of the expected age of natural menopause and does not pertain to conditions occurring in younger women. Younger women who experience spontaneous amenorrhea are considered to be of childbearing potential.

Women of reproductive potential may be enrolled into the study. However, female patients must agree to remain abstinent or use (or have their partner use) adequate contraception during the time period starting 2 weeks prior to enrollment through 6 months from the last vaccination dose. Acceptable methods of birth control include use of hormonal contraceptives, intrauterine device (IUD), diaphragm combined with spermicidal agent, contraceptive sponge, bilateral tubal ligation, condoms combined with spermicidal agent, or abstinence. Simultaneous use of two reliable forms of contraception is recommended. Females of reproductive potential must have been consistently using these barriers for at least 2 weeks prior to screening to be eligible for randomization.

If there is any question that a patient will not be reliable in the use of the appropriate contraceptive methods, the patient should not be enrolled into the study. Patients must be completely informed of the unknown risk of the vaccine during pregnancy and agree not to become pregnant during the time they enter the study through 6 months from the last vaccination dose.

